10.3 Scales: Rules for Scoring and Handling of Missing Data

10.3.1 YMRS

The YMRS is utilized as the primary efficacy assessment of a subject's level of manic symptoms. The YMRS consists of 11 items: 1) elevated mood, 2) increased motor activity-energy, 3) sexual interest, 4) sleep, 5) irritability, 6) speech (rate and amount), 7) language-thought disorder, 8) content, 9) disruptive-aggressive behavior, 10) appearance, and 11) insight. Seven items are rated on a 0- to 4-scale, while four items (Items 5, 6, 8, and 9) are rated on a 0- to 8-scale with 0, 2, 4, 6, and 8 being the possible scores (twice the weight of the other items). For all items, 0 is the "best" rating and the highest score (4 or 8) is the 'worst' rating. The YMRS Total Score is the sum of ratings for all 11 items; therefore, possible total scores range from 0 to 60. The YMRS Total Score is set to be missing if less than 9 of the 11 items are recorded. If 10 of the 11 items are available and the item missing is from items 5, 6, 8 or 9, then the YMRS Total Score is the sum of scores for items 1 to 4, 7, 10 to 11 plus the mean of the recorded items from 5, 6, 8 and 9 times four. If 10 of the 11 items are available and the item missing is from items 1 to 4, 7, 10 to 11, then the YMRS Total Score is the sum of scores for items 5, 6, 8 and 9 plus the mean of the recorded items from 1 to 4, 7, 10 to 11.

times seven. If 9 of the 11 items are available and both missing items are from items 5, 6, 8 and 9, then the YMRS Total Score is set to be missing. If 9 of the 11 items are available and both missing items are from items 1 to 4, 7, 10 to 11, then the Total Score was the sum of scores for items 5, 6, 8 and 9 plus the mean of the recorded items from 1 to 4, 7, 10 to 11 times seven. If 9 of the 11 items are available and one of the missing items is from items 1 to 4, 7, 10 to 11, and one of the missing items is from items 5, 6, 8 and 9, then the YMRS Total Score is the mean of the recorded items from 5, 6, 8 and 9 times four, plus the mean of the recorded items from 1 to 4, 7, 10 to 11 times seven. All imputed scores are rounded to the first decimal place.

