3.7.2.1 Young-Mania Rating Scale

The YMRS consists of 11 items assessing the core symptoms of mania⁸ and is based on questions asked of the subject regarding his or her clinical condition. Additional information is based upon clinical observations made during the course of the clinical interview. Each item has 5 defined categories of severity with 4 items graded on a 0 to 8 scale (irritability, speech, content, and disruptive-aggressive behavior) and 7 items graded on a 0 to 4 scale. A copy of the YMRS is provided in Appendix 7.

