9.2 Data Collection

During each subject's visit to the clinic, a clinician participating in the trial will record progress notes to document all significant observations. At a minimum, these notes will contain:

- Documentation of the informed consent process, including any revised consents;
- Documentation of the investigator's decision to enroll the subject into the trial, the review of all inclusion/exclusion criteria prior to IMP administration, and confirmation of the subject's actual participation in the trial;
- The date of the visit and the corresponding Visit or Day in the trial schedule;
- General subject status remarks, including any significant medical findings. The severity, frequency, and duration of any AEs and the investigator's assessment of relationship to IMP must also be recorded;
- Any changes in concomitant medications or dosages;
- A general reference to the procedures completed;
- The signature (or initials) and date of all clinicians who made an entry in the progress notes.

In addition, any contact with the subject via telephone or other means that provides significant clinical information will also be documented in the progress notes as described above.

Source documents and source data will be captured electronically in this trial, and will meet the same fundamental elements of data quality (eg, attributable, legible, contemporaneous, original, and accurate) as paper records. These data will be collected

into a system that is fully validated. Changes to the data will be captured by an automatic audit trail.

The trial site will be given a tablet to directly record subject data and clinical observations on electronic forms. Designated trial site staff will not be given access to the system until they have been appropriately trained. Information to be originally captured and reviewed electronically shall include details of the subject visit and the protocol-required assessments performed as a part of these visits, medical history, AEs, and concomitant medications. Because this trial is using an electronic source record as the original point of data capture, there is no additional data entry step for the trial site for data collected directly into the application - rather, the electronic source record directly populates the trial database.

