Appendix 7 **Young-Mania Rating Scale**

What is the YMRS?

The YMRS is an 11-item scale which aims to provide a continuous measure rating the intensity of symptoms associated with mania. The YMRS was developed as an instrument to be used by clinicians. Young et al. suggested the ratings should be based on a 15-30 minute clinical interview which takes into consideration the patients' subjective report as well as the raters' observation. Young and his collaborators intended to improve upon previous scales by providing a larger number of items for increased sensitivity and better rater reliability through the use of defined anchor points.

Optimizing the YMRS for Research

To reduce sources of error associated with the YMRS, we would like you to use the attached scripted interview when administering the YMRS.

Conventions for the YMRS

- Use the extremes of the rating scale when the anchor points accurately describe the patient's condition. Zero really means the symptom is absent. The YMRS extremes are not meant to be held in reserve for the worst imaginable case. Rather, they include common manifestations of severe manic states.
- Always score in whole numbers, but note items 5, 6, 8, and 9 not only allow but also encourage scores between the defined anchor points.
- When in doubt between two ratings, assign the higher rating, or, on 0 – 8 scaled items, the middle rating.
- Be sure that you have enough time to conduct the interview properly – you may be able to complete the YMRS in 15 minutes, but interviews with symptomatic patients often require 30-45 minutes.
- Clarify the patient's understanding and usage of terms like "paranoid", "irritable", "hyper", and "sexual interest".

YMRS

DIRECTIONS

For each item below begin inquiry using the script. Ask additional questions if necessary to assign ratings. Rate each item using your judgement in addition to the patient's self report. Also, include any information obtained outside the interview (e.g., reports by family members, etc.).

The purpose of each item is to rate the severity of that abnormality in the patient. When several keys are given for a particular grade of severity, the presence of only one is required to qualify for that rating.

The keys provided are guides. One can ignore the keys if that is necessary to indicate severity, although this should be the exception rather than the rule.

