Scoring between the points given (always in whole points) is possible and encouraged after experience with the scale is acquired.

I will now be asking you questions to rate symptoms you may have had during the past week.

Information given in italics is intended to guide the interviewer in clarifying severity levels for each rating.

1. Elevated Mood

The first item probes for the presence of elevated mood. Using the questions below you will inquire about "high" or elevated mood, euphoria, self-confidence, optimism, and inappropriate humor.

This past (week or seven days) how has your mood been?

Did you feel optimistic about the future? (Was there reason to feel that way?)

Distinguish here between healthy optimism, e.g., a sense that things might be improving, from an overly optimistic viewpoint. For example, a patient who is recovering from a depressive episode and is feeling simply less discouraged, would not be rated as "overly optimistic." Take into account if there is reason for the patient to feel more optimistic.

Did you feel especially self confident (especially good about yourself)?

Rate here a sense of feeling particularly good or self-confident about one's abilities.

Were there any times you felt too good or even a little high? [If yes] Were the good days really too good, or just better than the bad days?

It is helpful here to inquire if others noticed that they were in more than just a good mood. If necessary, clarify the use of the term feeling "high," e.g., feeling on top of the world, feeling so good it is like being on a drug, etc. Remember, you are rating abnormal mood elevation, not simply an improvement from depressed mood.

Were there times when you laughed about things you ordinarily wouldn't find funny? Or did you laugh or joke about things that other people don't find funny (or thought in poor taste)?

You are probing here for an increased or inappropriate sense of humor. You may clarify this item by asking if, in retrospect, they viewed their behavior as inappropriate or if others seemed offended by their humor. Also, use your clinical judgement in rating whether the use of humor was inappropriate (e.g., making sexual jokes or innuendos at work).

0 Absent

A rating of 0 indicates that there has been no observed or reported mood elevation in the past week. The symptom is completely absent.

1 Mildly or possibly increased on questioning

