Probe here for paranoia.

Did you have any thoughts that didn't make sense to other people?

Did you have any hallucinations?

It is important to clarify use of the term hallucinations, e.g., did you see things that others couldn't see or did you hear things that others couldn't hear?

0 Normal

A rating of 0 indicates that the patient has exhibited none of the symptoms counting towards this item.

1

2 Questionable plans, new interests

A rating of 2 indicates that the patient has engaged in some new plans or interests of a possibly questionable nature, e.g., planned a spontaneous vacation (within budget); scheduled more social plans than usual; shopped more than usual without spending extravagantly. You must take into account the patient's typical budget and financial situation when judging monetary decisions. Impulsive purchases clearly out of line with patient's budget should be rated a 3 or higher depending on level of excessiveness.

3

4 Special project(s); hyperreligious

A rating of 4 indicates that the patient has taken on new projects or plans of a clearly questionable nature, e.g., spending impulsively and out of budget, impulsively building an addition to one's home without prior planning, etc. A rating of 4 would also be warranted for a sudden increase in religious participation, e.g., an individual who usually attends church on a weekly basis has attended every day in the past week and not due to some external stressor or crisis, i.e., a mother who attends church on a daily basis to pray for her child who has recently been hospitalized would not qualify as "hyper-religious".

5

6 Grandiose or paranoid ideas; ideas of reference

A rating of 6 is warranted if the patient describes having special powers or abilities, e.g., being able to predict the future or being the "best in the world" at a particular talent or ability. An example might be the student who believes that the insights in his term paper will radically alter his professor's life. A rating of 6 might also be given if a patient reports finding special meaning or significance in everyday situations (e.g., seeing a particular sign on the street and "knowing" that it is pointing him towards a new career. If the patient exhibits clearly paranoid thinking, a rating of 6 is also justified. Be sure to clarify the patient's use of the term paranoid, e.g., use your judgment to ascertain evidence of true vs. imagined negative intentions of others.

7

8 Delusions; hallucinations

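### Does listing only even scores for YMRS items 5, 6, 8 and 9 spoil the primary-endpoint total, when the rating form allows odd ones?

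*SAP*

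**What the plan says.** The YMRS Total Score carries the primary endpoint (change from baseline to Day 21) and the entry criterion of at least 24 at screening and baseline. Three places give its scoring in nearly the same words: Protocol 7.3, SAP 5.2 and SAP 10.3.1. Each says that items 5, 6, 8 and 9 are "rated on a 0- to 8-scale with 0, 2, 4, 6, and 8 being the possible scores", and each then gives the rule for the total: "The YMRS Total Score is the sum of ratings for all 11 items". Rules for one or two missing items follow.

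Protocol 3.7.2.1 gives every item five defined severity categories, with "4 items graded on a 0 to 8 scale (irritability, speech, content, and disruptive-aggressive behavior" and the other seven on 0 to 4. It refers the reader to Appendix 7 and sets no even-only limit.

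Appendix 7 goes further. Its conventions tell raters to "note items 5, 6, 8, and 9 not only allow but also encourage scores between the defined anchor points". Its directions add: "Scoring between the points given (always in whole points) is possible and encouraged after experience with the scale is acquired". A rater in doubt is told to "assign the higher rating, or, on 0 – 8 scaled items, the middle rating". The values 1, 3, 5 and 7 are printed, without descriptions, under all four items. The guidance for item 8 says that impulsive purchases clearly beyond the patient's "budget should be rated a 3 or higher depending on level of excessiveness".

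**The concern.** Read literally, the scoring text calls impossible the very ratings that the form invites. Neither redaction nor superseded wording explains this, since both texts are current. The four items supply up to 32 of the 60 points of the primary outcome, and SAP 10.3.1 is where a programmer would look for valid values.

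Protocol 9.2 adds to the worry. Assessments are captured electronically, and "there is no additional data entry step for the trial site for data collected directly into the application". A field limited to even values would act at the moment of rating, and no separate source would hold what the rater meant to enter. If the list were enforced, an odd rating might be pushed to a neighbouring even value or treated as not recorded. The second could prorate the total or set it to missing.

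**Working it through.** **Inputs.** Seven items scored 0 to 4 and four scored 0 to 8 (Protocol 3.7.2.1; SAP 10.3.1). Stated range of the total: 0 to 60 (SAP 10.3.1). Printed options on each of items 5, 6, 8 and 9: 0 to 8 (Protocol Appendix 7).

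**1. The plan's own figure.** Maximum total = 7 × 4 + 4 × 8 = 28 + 32 = 60. This is the same whether the four items take five values or nine, so the stated range is correct either way. So is the remark that these items carry twice the weight of the others (8 against 4).

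**2. Size of the textual conflict.** Printed options: 4 × 9 = 36. Options in the stated list: 4 × 5 = 20. Left out: 16, and 16/36 = 44%. The middle of two adjacent anchors is always odd: (0+2)/2 = 1, (2+4)/2 = 3, (4+6)/2 = 5, (6+8)/2 = 7. The 44% counts printed options. It does not say how often raters choose them.

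**3. Does any rule use the list?**
- *Complete scale.* The total is the sum of the ratings. With items 5, 6, 8 and 9 rated 5, 3, 5, 3 and 14 points elsewhere, the total is 16 + 14 = 30. Nothing in the rule asks whether a rating is even.
- *One of the four items truly missing.* The rule takes the mean of the three recorded items times four. With 5, 3 and 4 recorded, that is (12/3) × 4 = 16. The result stays within 0 to 32 for any whole-number ratings.
- *What triggers the missing-item rules.* They depend on items being recorded or available. A 3 entered on item 8 is both.
- *Model.* The MMRM is fitted to change in the total and does not use item levels.

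The effect of an odd rating under the rules as written is therefore zero.

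**4. What enforcing the list would do, though no stated rule does so.**
- *Forcing to an even neighbour.* Each odd item moves by 1 point, so the example total of 30 becomes 34 if all four go up and 26 if all go down.
- *Treating odd as not recorded.* Ratings 5, 2, 2, 2 plus 13 elsewhere total 24. Dropping the 5 gives 13 + (6/3) × 4 = 21.0. Two dropped items set the total to missing.
- *Chance of a missing total under that treatment.* If each of the four items is odd independently with probability q, the chance is 1 − (1−q)⁴ − 4q(1−q)³. This gives 1.4% at q = 0.05, 18.1% at q = 0.20 and 52.5% at q = 0.40. Both q and independence are assumptions; the documents give no frequency of odd ratings.

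These figures show what misuse of the clause would cost. They do not describe the plan.

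**The case for a change.** The best case for a change is that a pre-specified rule for the primary outcome should not rely on readers passing over its words. The clause speaks of possible scores, not of anchors. The field definitions and edit checks are not shown, so nobody can tell from the documents whether someone built the list into the system. Correcting the phrase would be easy.

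The first part stands: the wording is wrong and Appendix 7 is the better authority. The rest carries less weight. Protocol 9.2 says how data reach the database and nothing about permitted YMRS values. The nearest visible evidence points the other way. The rationale in Protocol Appendix 15 says that the appendix scales were brought into line with the licensed versions, that grading and scoring did not change, and that the correct versions had been in use since the trial began. This does not prove how the fields were set, but it supports the view that raters had the nine-point form.

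A wording change would not protect against a restrictive field in any case. A field that blocked odd entries would have to be caught during data collection; a check just before unblinding could not recover the ratings. That is a matter of system validation. Nor is the edit quite free on the protocol side, because Protocol section 13 requires any permanent change to be handled as an amendment.

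**Conclusion.** No change to the plan is needed. The clause is a clerical slip: it gives the five anchor points, which match the five defined categories in Protocol 3.7.2.1, as if they were the only scores. An analyst who follows the stated sum obtains the correct Total Score from any whole-number ratings. The 0 to 60 range, the proration rules, the model, the significance level and the sample size are unaffected, and the effect on the primary endpoint is zero.

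This rests on two assumptions. First, odd ratings are stored and summed as rated, which is what the sum rule says. Second, the text blacked out in Protocol 7.3 and SAP 5.2 contains no separate rule for odd scores. SAP 10.3.1 repeats the scoring in full, without redaction, and has none. If either assumption failed, the size of the effect would depend on how often raters chose odd scores, which the documents do not report.

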10.3.2 CGI-BP

The CGI-BP scale refers to the global impression of the subject with respect to bipolar disorder. The scale rates the subject's Severity of Illness (CGI-BP severity of illness: mania, depression, and overall bipolar illness) and based on a 7-point scale and rates the subject's Change from Baseline (CGI-BP Change from Baseline: mania, depression, and overall bipolar illness) based on a 7-point scale. CGI-BP severity of illness items are: 1 = normal, not at all ill, 2 = minimally ill, 3 = mildly ill, 4 = moderately ill, 5 = markedly ill, 6 = severely ill, 7 = very severely ill. CGI-BP Change from Baseline items are: 1 = very much improved, 2 = much improved, 3 = minimally improved, 4 = no change, 5 = minimally worse, 6 = much worse, 7 = very much worse. The CGI-BP Change from Baseline is not assessed at the baseline visit. At each visit other than baseline, the Change from Baseline will be judged with respect to subject's condition at baseline.

10.3.3 CCI

10.3.4 CCI

CCI
[REDACTED]

10.3.5 CCI

[REDACTED]
[REDACTED]
[REDACTED]
[REDACTED]
[REDACTED]
[REDACTED]
[REDACTED]
[REDACTED]
[REDACTED]
[REDACTED]

10.3.6 CCI

[REDACTED]
[REDACTED]

10.3.7 CCI

[REDACTED]
[REDACTED]
[REDACTED]
[REDACTED]
[REDACTED]
[REDACTED]
[REDACTED]
[REDACTED]

Appendix 1 Criteria for Identifying Vital Signs of Potential Clinical Relevance

Variable	Criterion Value ^a	Change Relative to Baseline ^a
Heart Rate ^b	> 120 bpm < 50 bpm	≥ 15 bpm increase ≥ 15 bpm decrease
Systolic Blood Pressure ^b	> 180 mmHg < 90 mmHg	≥ 20 mmHg increase ≥ 20 mmHg decrease
Diastolic Blood Pressure ^b	> 105 mmHg < 50 mmHg	≥ 15 mmHg increase ≥ 15 mmHg decrease
Orthostatic Hypotension	≥ 20 mmHg decrease in systolic blood pressure and a ≥ 25 bpm increase in heart rate from supine to sitting/standing	Not Applicable (baseline status not considered)
Weight	-	≥ 7% increase ≥ 7% decrease

^a In order to be identified as potentially clinically relevant, an on-treatment value must meet the “Criterion Value” and also represent a change from the subject’s baseline value of at least the magnitude shown in the “Change Relative to Baseline” column.

^b As defined in “Supplementary Suggestions for Preparing an Integrated Summary of Safety Information in an Original NDA Submission and for Organizing Information in Periodic Safety Updates,” FDA Division of Neuropharmacological Drug Products draft (2/27/87).

Appendix 2 Criteria for Identifying Laboratory Values of Potential Clinical Relevance

Laboratory Tests		Criteria
Chemistry		
AST (SGOT)		$\geq 3 \times$ upper limit of normal (ULN)
ALT (SGPT)		$\geq 3 \times$ ULN
Alkaline phosphatase		$\geq 3 \times$ ULN
Lactate dehydrogenase (LDH)		$\geq 3 \times$ ULN
Blood urea nitrogen (BUN)		≥ 30 mg/dL
Creatinine		≥ 2.0 mg/dL
Uric Acid		
Men		≥ 10.5 mg/dL
Women		≥ 8.5 mg/dL
Bilirubin (total)		≥ 2.0 mg/dL
Creatine phosphokinase (CPK)		$\geq 3 \times$ ULN
Prolactin		$>$ ULN
Hematology		
Hematocrit		
Men		$\leq 37\%$ and decrease of ≥ 3 percentage points from Baseline
Women		$\leq 32\%$ and decrease of ≥ 3 percentage points from Baseline
Hemoglobin		
Men		≤ 11.5 g/dL
Women		≤ 9.5 g/dL
White blood count		$\leq 2,800/\text{mm}^3$ or $\geq 16,000/\text{mm}^3$
Eosinophils		$\geq 10\%$
Neutrophils		$\leq 15\%$
Absolute neutrophil count		$\leq 1,000/\text{mm}^3$
Platelet count		$\leq 75,000/\text{mm}^3$ or $\geq 700,000/\text{mm}^3$
Urinalysis		
Protein		Increase of ≥ 2 units
Glucose		Increase of ≥ 2 units
Casts		Increase of ≥ 2 units
Additional Criteria		
Chloride		≤ 90 mEq/L or ≥ 118 mEq/L
Potassium		≤ 2.5 mEq/L or ≥ 6.5 mEq/L
Sodium		≤ 126 mEq/L or ≥ 156 mEq/L
Calcium		≤ 8.2 mg/dL or ≥ 12 mg/dL
Glucose		
Fasting		≥ 100 mg/dL
Non-Fasting		≥ 200 mg/dL
Total Cholesterol, Fasting		≥ 240 mg/dL
LDL Cholesterol, Fasting		≥ 160 mg/dL
HDL Cholesterol, Fasting		
Men		< 40 mg/dL
Women		< 50 mg/dL
Triglycerides, Fasting		≥ 150 mg/dL

Appendix 3**Criteria for Identifying ECG Measurements of Potential Clinical****Relevance**

[figure not shown]
Variable	Criterion Value ^a	Change Relative to Baseline ^a
Rate		
Tachycardia	≥ 120 bpm	increase of ≥ 15 bpm
Bradycardia	≤ 50 bpm	decrease of ≥ 15 bpm
Rhythm		
Sinus tachycardia ^b	≥ 120 bpm	increase of ≥ 15 bpm
Sinus bradycardia ^c	≤ 50 bpm	decrease of ≥ 15 bpm
Supraventricular premature beat	all	not present → present
Ventricular premature beat	all	not present → present
Supraventricular tachycardia	all	not present → present
Ventricular tachycardia	all	not present → present
Atrial fibrillation	all	not present → present
Atrial flutter	all	not present → present
Conduction		
1° atrioventricular block	PR ≥ 200 msec	increase of ≥ 50 msec
2° atrioventricular block	all	not present → present
3° atrioventricular block	all	not present → present
Left bundle-branch block	all	not present → present
Right bundle-branch block	all	not present → present
Pre-excitation syndrome	all	not present → present
Other intraventricular conduction block ^d	QRS ≥ 120 msec	increase of ≥ 20 msec
Infarction		
Acute or subacute	all	not present → present
Old	all	not present → present
		≥ 12 weeks post study entry
ST/T Morphological		
Myocardial Ischemia	all	not present → present
Symmetrical T-wave inversion	all	not present → present
Increase in QTc	QTcF ≥ 450 msec (men) QTcF ≥ 470 msec (women)	

^a In order to be identified as potentially clinically relevant, an on-treatment value must meet the “Criterion Value” and also represent a change from the subject’s baseline value of at least the magnitude shown in the “Change Relative to Baseline” column.

[figure not shown]
^b No current diagnosis of supraventricular tachycardia, ventricular tachycardia, atrial fibrillation, atrial flutter, or other rhythm abnormality.

^c No current diagnosis of atrial fibrillation, atrial flutter, or other rhythm abnormality.

^d No current diagnosis of left bundle branch block or right bundle branch block.

CCI

CCI

CCI

Horizontal bar chart showing CCI values for 100 samples across four categories: C1, C2, C3, and C4. The y-axis is labeled "Sample" and ranges from 1 to 100. The x-axis is labeled "CCI" and ranges from 0 to 100. Each sample has four bars representing the C1, C2, C3, and C4 categories. The bars are black with white outlines. The C1 and C2 bars are consistently the longest, while C3 and C4 are shorter. The C1 bar for sample 100 is the longest, exceeding the 100 mark on the x-axis.

CCI
